Cancer clinical trials are essential for testing the safety and efficacy of promising treatments and translating new knowledge into tangible benefits for patients; they also represent state-of-the-art treatment for individuals with cancer.^{1,2} However, only a small percentage of cancer patients ever enroll in a trial.^{3,4} Estimates of the proportion of trials that fail to meet scientific objectives because of insufficient accrual range from 22-50%.^{5,6} Low accrual jeopardizes researchers' ability to assess the safety and effectiveness of new approaches to cancer care, wastes resources, and precludes follow-up studies.^{6,7}

Under-enrollment is an even greater problem among minorities, particularly African Americans,^{4,8,9,10} despite NIH requirements to include minorities in clinical research.¹¹ Minority under-enrollment limits the generalizability of findings,^{10,12} and, given the Institute of Medicine's recommendation that every individual with cancer should have access to high quality clinical trials,² minority under-enrollment represents a racial/ethnic disparity in cancer care that may lead to disparities in treatment outcomes and survival.^{1,13,14}

Under-enrollment of African Americans and other minorities is often attributed to patients' negative attitudes toward trials,¹⁵⁻¹⁷ but research suggests a more complicated picture.^{10,18-21} National and system factors, such as a lack of available trials, strict eligibility criteria, and competing demands on under-resourced hospitals also present significant barriers that likely have a disproportionate effect on minority enrollment.^{2,8,19,22-24} Several national, regional, and consortia efforts are addressing either patient or system factors.^{10,20,25,26} However, even when medical institutions have a trial infrastructure and trials are available, physicians are often unwilling or unprepared to discuss trials with some patients, and some patients are mistrustful of physicians or of trials.

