We plan to recruit a total of **440 patients**, including 220 African Americans and 220 White patients. We will recruit patients in the order they are identified as eligible and interested, but we will attempt to recruit no more than **60 total** patients per physician, half who self-identify as Black/African American and half who self-identify as White. Further, we will recruit family members and other health care providers that may appear in our video recordings. We anticipate recruiting a total of **200 family members** and **100 other health care providers**. Considering the fact that many patients may never become eligible for an available trial or may leave the study for medical or social reasons, we estimate that approximately 216 of these participants will be eligible for a clinical trial. Thus, **our estimated sample for the primary analyses is 216 patients who will be video recorded discussing a trial with a participating physician**. We will recruit half of the patient sample (i.e., 220 AA and White men) as quickly as possible following their physician's consent at the beginning of data collection (the first 20 months/pre-physician intervention). These patients will actively participate until they either receive a trial offer or until the physician intervention is implemented. We will recruit the second half of the patient sample

(also 22) AA and White men) immediately following the physician intervention; these patients will participate actively until they receive a trial offer or until data collection ends.

[figure not shown]
Study Design, Interventions, and Measures

Study Design Overview (See Figure 2). This 5-year study involves two related interventions and research designs conducted over a 42-month data collection period. These interventions begin after IRB approval is received and physicians are consented.

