The first intervention is a randomized controlled trial focused on patients. This intervention is broken into two separate but identical parts, in which half of the patient sample participates before the physician intervention, and the other half participates after the physician intervention. In the first part, patients of participating physicians will be recruited and tracked until they become eligible for a trial, at which time they will be randomized into an intervention or usual care group. They will continue their participation until: they receive a trial offer, or they have four interactions with their physician without receiving an offer. Regardless of the number of interactions, this group of patients will discontinue their active participation when the physician intervention begins. Thus, these patients will participate for a maximum of 20 months. In the second part, which occurs after the physician intervention has been conducted, the remaining half of the patient sample will be recruited and tracked, and eligible patients will be randomly assigned to the two groups. Again, their participation will continue until they receive a trial offer, they have four interactions with their physician without an offer, or data collection ends. These patients will, thus, also participate for a maximum of 20 months. We will utilize a block-randomized design in which physicians are treated as blocks and patients are randomized to a group.

The second intervention is a within-subjects interrupted time series quasi-experiment focused on physicians.³⁰ Physicians will be recruited at the beginning of data collection, prior to any patient recruitment (i.e., once IRB approval has been received—approximately nine months after the formal start date of this grant award). In this within-subjects design, physicians provide pre-intervention data for 20 months, then receive the intervention and continue their participation for another 20 months (i.e., until the end of data collection). The same physicians will remain in the study throughout data collection; thus they will provide both pre intervention and post intervention data that will be used to examine the effectiveness of the physician-focused intervention.

Figure 2: Study Design and Procedures Overview

Patient Procedures, Measures, and Intervention

Patient Procedures.

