Power and Sample Size Estimates. A within-subject design is used to evaluate the physician intervention and a randomized control trial is used to evaluate the patient intervention. However, the outcomes of both interventions will be modeled at the patient level in a single model. We used the person-level multi-site/block trial design within Optimal Design to conduct power analyses because the unit of analysis is the patient-physician visit and data from these visits will likely be more similar within physicians than between physicians. The first power analysis is based 216 patients not lost to attrition, who should be eligible for clinical trials and thus randomized into the patient-level intervention. (See Participants and Recruitment—p. 7) We define the *primary outcome* of our study as patients' decisions to enroll in clinical trials, where a "success" is defined as a patient deciding to enroll. Our primary objective (Aim 1) is to examine the extent to which patient- and physician-level interventions affect physician and patient trial-related decisions, and thus we seek a sample size that gives us sufficient power to detect both the main effect of intervention and important interaction effects. We chose GEE power analysis for nested binomial outcomes with within-cluster treatments⁶⁶ as the best available model to estimate power for our primary objective; such estimates are lacking for HLM models. With 24 physicians and 9 patients per physician (i.e., 216 patients), a Type I error rate (α) of .05, and ICC of .05, and probability of success under the null hypotheses (p_{H_0}) of .25, we are well powered to detect p_H of .35 ($b = 0.48$, odds-ratio = 1.61) with power > .99. Our secondary objective, (i.e., Aim 2) is to examine whether patient race influences the effectiveness of either patient- or physician-level interventions on our primary outcome, and we remain well

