We will use Multi-Level Models (MLMs) that include separate variables identifying both interventions, as well as a variable indicating the interaction between the two phases. This model allows us to examine the main effect of each intervention, and multiplicative effects of having been exposed to both interventions. For purposes of clarity, we discuss hypotheses for each intervention separately, but as already noted, they will be tested in the same MLMs. We will model most outcomes (specifically, patients' perceptions of patient-centeredness, perceived involvement in care, trust in physician, and team perceptions; patient active participation, and physician patient centeredness, patient understanding of informed consent) as continuous variables. We will use binomial logistic models for binary outcomes (e.g., trial offer) and multinomial logistic regression for categorical outcomes (e.g., patients' self-reported participation decision - "yes", "no", "undecided"). We will also explore whether a single model best captures the meditational processes for both Black and White patients or separate models are needed.

Models for Aim 1: As we have described the objectives and outcomes above, here we generally describe the models that will be used to test support for our hypotheses. All outcomes, and coefficients for each of the intervention effects and interactions between them, will be modeled at the patient level of the model (level-1); that is, they will be nested within physicians (level-2). We will use one MLM for each outcome to test the three Aim 1 hypotheses. We use this particular approach to examine the interventions' effects because it is believed that the two interventions will not only work independently, but also interactively. Thus, we use a model that simultaneously controls for the main and interactive effects of both interventions as we examine their unique contributions.

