Control variables: At the patient level of the model, we will control for factors such as decisional control preferences, relevant attitudes, health literacy, number of boosters received, disease severity, co-morbidities, whether there is an available clinical trial for the patient, and if so, characteristics of the trial (e.g., difficulty, complexity). At the physician level, we will control for relevant racial and professional attitudes, and decisional control preferences. Because the physician-focused phase involves a quasi-experimental design, we will also control factors that might threaten the internal validity of the intervention, such as time since study has begun, and number of previous interactions between patients and physicians.

Hypothesis 1a. Outcomes will be significantly improved in the patient intervention group, relative to the usual care group. To test hypothesis 1a, we will fit separate MLMs to examine continuous and binary outcomes assessed during or after each visit in which a trial was discussed. The focal independent variable will be the dummy-coded variable indicating whether the patient was in the usual care or intervention group. Support for hypothesis 1a will be indicated by a significant coefficient for this independent variable (i.e. intervention/usual care).

Hypothesis 1b. Outcomes will be significantly improved for patients after the physician intervention, as compared to outcomes before the physician intervention. The focal independent variable is the dummy-coded variable indicating whether or not the patient's physician has received the physician intervention at the time of the clinic visit. Note that this variable is a within-subject variable among the physicians; however, because we theorize that the patient-physician communication quality is central to offers and acceptance of clinical trials, this variable is introduced in the model at level-1 (patients). Support for hypothesis 1b will be indicated by a significant physician-intervention coefficient (i.e., pre/post physician intervention).

Hypothesis 1c. The combined effects of the two interventions will be multiplicative, rather than simply additive. The focal independent variable is the dummy coded variable for the product interaction term in the model. We expect the physician intervention to be more effective among patients who received the patient intervention; we expect a statistically significant positive coefficient for the interaction term.

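### The randomised comparison is set up on men or visits with a trial discussion, which is known only after randomisation; no analysis of all randomised men is stated

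*Combined protocol and SAP*

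**What the plan says.** All references are to the combined protocol and SAP.

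- **Randomisation.** Under Patient Procedures, Time 1, a man found potentially eligible completes a questionnaire and is then randomised, before his clinic visit. Whether a trial was discussed is learned later, from the physician's post-visit report and from raters of the recording (Clinic Visits; Observational Measures).
- **Hypothesis 1a.** The plan states that "we will fit separate MLMs to examine continuous and binary outcomes assessed during or after each visit in which a trial was discussed". Models for Aim 1 uses one model per outcome for all three Aim 1 hypotheses, so the restriction appears to reach 1b and 1c as well.
- **Participants and Recruitment.** Here "our estimated sample for the primary analyses is 216 patients who will be video recorded discussing a trial with a participating physician". The sentence before it gives 216 as the number expected to be eligible.
- **Power and Sample Size Estimates.** The calculation rests on "216 patients not lost to attrition, who should be eligible for clinical trials and thus randomized into the patient-level intervention". A success "is defined as a patient deciding to enroll", which is binary.
- **Model types** (the paragraph before Models for Aim 1). Trial offer is modelled as binary. The yes/no/undecided decision is assigned to "multinomial logistic regression for categorical outcomes".
- **Men without an offer.** Study Design Overview ends participation if "they have four interactions with their physician without receiving an offer". In the first phase, "this group of patients will discontinue their active participation when the physician intervention begins". How these men enter the analysis is not said.

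**The concern.** A discussion happens after randomisation and may depend on the arm. The booklet gives men trial-related questions to ask, so it may prompt discussions that would not otherwise occur. Restricting the analysis to discussed visits then compares two groups that randomisation did not form, in the only randomised comparison the study has. It also discards benefit that arises because more men get a discussion at all. For trial offers the problem is sharper: a discussion is a step on the way to an offer, so an analysis limited to discussed visits cannot capture the full effect on offers.

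The two descriptions of the 216 agree only if every retained randomised man has a recorded discussion. The plan's own premise makes that doubtful. Background and Specific Aims says that "even when medical institutions have a trial infrastructure and trials are available, physicians are often unwilling or unprepared to discuss trials with some patients", and the four-visit rule provides for men who never receive an offer.

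If the booklet changes neither the rate nor the mix of discussions, the contrast is not biased, but it describes discussed men only.

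**Working it through.** **Inputs from the plan (Power and Sample Size Estimates).** 24 physicians × 9 patients = 216 men; success probabilities .25 and .35.

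**The plan's own figure.** OR = (.35/.65)/(.25/.75) = 1.615. The plan prints 1.61, so this reproduces.

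**Assumptions.** Equal arms of 108. Nobody decides to enrol without a discussion. Clustering is ignored. The discussion rates d0 (usual care) and d1 (intervention) are all assumed, because the plan gives none. The plan also does not say whether .25 and .35 are per randomised man or per man with a discussion, so both readings are shown.

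**Size of the discussed set.** n = 108 × (d0 + d1), which equals 216 only when d0 = d1 = 1.

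**A. The rates are per randomised man.** Rate among discussed men = rate / d. The rate ratio among them is 1.4/(d1/d0). The OR in all randomised men is 1.62.

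| d0 / d1 | Rates among discussed men | n | OR among discussed men |
|---|---|---|---|
| .50 / .50 | .500 vs .700 | 108 | 2.33 |
| .50 / .55 | .500 vs .636 | 113 | 1.75 |
| .90 / .90 | .278 vs .389 | 194 | 1.65 |
| .60 / .65 | .417 vs .538 | 135 | 1.63 |
| .90 / .95 | .278 vs .368 | 200 | 1.52 |
| .80 / .90 | .3125 vs .389 | 184 | 1.40 |
| .50 / .70 | .500 vs .500 | 130 | 1.00 |

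The rows with equal rates show a change of estimand, not bias.

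**B. The rates are per discussed man.** The OR among discussed men is 1.62 by construction. Rate in all randomised men = rate × d.

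| d0 / d1 | Rates in all randomised men | OR in all randomised men |
|---|---|---|
| .50 / .50 | .125 vs .175 | 1.48 |
| .90 / .90 | .225 vs .315 | 1.58 |
| .90 / .95 | .225 vs .3325 | 1.72 |
| .80 / .90 | .200 vs .315 | 1.84 |

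**C. Mechanism.** The booklet raises discussion from .80 to .90 and changes no man's decision once a trial is discussed. The added men decide to enrol with probability p. Usual care: .80 × .3125 = .25 per randomised man. Intervention: .25 + .10p per randomised man, and (.25 + .10p)/.90 among discussed men.

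| p | Intervention, all randomised | OR, all randomised | Intervention, discussed | OR, discussed |
|---|---|---|---|---|
| .10 | .26 | 1.05 | .289 | 0.89 |
| .3125 | .281 | 1.17 | .3125 | 1.00 |
| .50 | .30 | 1.29 | .333 | 1.10 |

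In the first row the direction reverses; in the second a real gain disappears.

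**A wider gap.** Take discussion at .60 vs .80, with men who would discuss anyway deciding to enrol at .25 in both arms. If the added men decide to enrol at 0, the discussed-set rate is (.60 × .25)/.80 = .1875 and the OR there is 0.69, although both arms stand at .15 per randomised man. If they do so at .50, the discussed-set OR is 1.36, against .15 vs .25 per randomised man.

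**The case against.** The best defence is that the text does not clearly restrict the primary outcome.

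- The Hypothesis 1a sentence names continuous and binary outcomes, while the decision is elsewhere multinomial.
- The Participants and Recruitment sentence calls itself an estimate and follows from a count of eligible men, so it may be a forecast in loose wording.
- The Hypothesis 1a clause can be read as saying when outcomes are measured, not which men are excluded.
- The control variables include trial availability, which would hardly vary if only discussed visits entered. Offer status is collected after every tracked visit.
- An effect of the booklet on the frequency of discussion is inferred; no section states it. The stated aim of increasing discussion belongs to the physician intervention, which is not randomised and reaches both arms in the second phase.
- Only offered men have the Time 3 interview, so for the others a decision would be assigned, not observed.

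Much of this stands as qualification. For the decision to enrol, the restriction rests on the recruitment sentence together with the binary definition of success, and the arm effect on discussion is plausible, not documented. But none of these points supplies a wider analysis set. Randomised men have all been screened as potentially eligible, so the availability covariate is only a hint. The timing reading still leaves men without a discussion unplaced. For trial offers the clause applies as written.

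**Conclusion.** The concern holds. Followed as written, the plan conditions its only randomised comparison on an event after randomisation and removes one route to trial offers. On the most generous reading, the primary analysis population is undefined, and two analysts could choose different ones after seeing the data. This must be fixed before analysis.

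The size and direction of any bias cannot be stated. Every discussion rate used above is an assumption, and the calculations are unclustered. They show that the discussed-set odds ratio can lie above or below the all-randomised one and can point the other way (0.89 against 1.05). If nearly all randomised men have a discussion, the distortion is small.

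**What to change.** - **Hypothesis 1a, and Participants and Recruitment:** state that the primary analysis of the decision to enrol, and the analysis of trial offers, include all randomised men by assigned arm. Men with no discussion or no offer count as not deciding to enrol, or as not offered. State how a man who leaves after randomisation with an unknown decision is handled.
- **Model types:** state that the primary test uses the binary success from the power section, with undecided counted as not a success. Make the multinomial model supportive.
- **Discussed-visit analyses:** keep them as supportive. Label outcomes that exist only after a discussion or offer (understanding of the trial offered, quality of trial-related communication) as conditional, non-randomised comparisons.
- **Power and Sample Size Estimates:** say whether 216 is the number randomised or retained. If retained, an assumed 5%, 10% or 20% loss means 216/.95 = 227, 216/.90 = 240 or 216/.80 = 270 randomised. Say also whether .25 and .35 are per randomised or per discussed man.
- **Reporting:** give discussion rates by arm and by phase.

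**Cost.** The change is one of wording in those four places, and the 216 and the .25/.35 rates may need restating. No new data collection is apparent: visit reports, recordings, the Time 2 and Time 3 reports and the Time 4 record review are already planned. The drawback is dilution by men never offered a trial, including first-phase men whose participation is cut off when the physician intervention begins.

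### Hypotheses 1a and 1b are judged by single dummy coefficients in a model that also holds their product; under 0/1 coding these are simple effects, not the main effects the plan names

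*Combined protocol and SAP*

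**What the plan says.** All three Aim 1 hypotheses are tested in one model. Models for Aim 1 states: "We will use one MLM for each outcome to test the three Aim 1 hypotheses". The paragraph just before it puts both intervention variables and their interaction in that model and claims: "This model allows us to examine the main effect of each intervention, and multiplicative effects of having been exposed to both interventions".

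The decision rules follow under the separate hypotheses:

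- **Hypothesis 1a:** "The focal independent variable will be the dummy-coded variable indicating whether the patient was in the usual care or intervention group". Then: "Support for hypothesis 1a will be indicated by a significant coefficient for this independent variable (i.e. intervention/usual care".
- **Hypothesis 1b:** "Support for hypothesis 1b will be indicated by a significant physician-intervention coefficient (i.e., pre/post physician intervention".
- **Hypothesis 1c:** judged by the product term, which is expected to be positive: "We expect the physician intervention to be more effective among patients who received the patient intervention".

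Power and Sample Size Estimates seeks "sufficient power to detect both the main effect of intervention and important interaction effects" and bases this on all 216 trial-eligible patients. Control variables adds, among others, "time since study has begun, and number of previous interactions between patients and physicians".

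No numeric codes, reference levels, centring or averaged contrast is given for the Aim 1 tests. Models for Aim 2 adds two-way race interactions and a three-way term, and again reads the race by patient-intervention question from a single coefficient.

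**The concern.** When a model contains a product term, the coefficient of one 0/1 dummy is that variable's effect where the other variable equals zero. It equals the effect averaged over both levels only if the interaction is zero, and the plan expects an interaction. If that expectation is right, both stated coefficients are smaller than the averaged effects. The Hypothesis 1a coefficient also draws on only about half of the randomised patients; the rest inform only covariate and variance estimates.

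A real patient-intervention effect could therefore be declared unsupported on the primary outcome although the full randomised sample would have shown it. Because the codes are unwritten, the Hypothesis 1a result could also turn on a coding choice made after the data are seen. The race by patient-intervention test has the same gap.

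**Working it through.** **Inputs from the plan.** 24 physicians with 9 patients each (216), alpha .05, ICC .05, success rates .25 and .35, stated power above .99. For continuous outcomes: d = .50, effect-size variance .05, stated power above .90. Half of the patient sample is recruited before and half after the physician intervention.

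**Assumptions.** 0/1 coding with usual care and pre-training as zero; 1:1 allocation; equal phases, so 216/4 = 54 per cell; two-sided test; variance multiplied by 1 - .05 = .95 for within-physician contrasts.

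**The plan's own figures.** The odds ratio (1.615) and b (0.480) reproduce. The binary power does not: 108 versus 108 gives .36 two-sided, or .38 with the .95 factor, and at most about .50 one-sided. The continuous power does reproduce: SE = sqrt((.05 + 4/9)/24) = .1435, .50/.1435 = 3.48, and the noncentral t with 23 df gives .915.

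**What the coefficients mean.** Let A be the patient intervention and P the post-training phase, with linear predictor b0 + b1·A + b2·P + b3·A·P.

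- b1 is the effect of A when P = 0, that is, before training.
- b2 is the effect of P when A = 0, that is, in usual care.
- The averaged effects are b1 + b3/2 and b2 + b3/2.

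**Hypothesis 1a, 25% versus 35% in both phases (log-odds 0.480).**

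- As written: SE = sqrt(.95 × (1/(54 × .1875) + 1/(54 × .2275))) = sqrt(.95 × .1802) = .414. Then .480/.414 = 1.16, power .21.
- Averaged: SE = .414/sqrt(2) = .293. Then .480/.293 = 1.64, power .37.

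**Hypothesis 1a with an interaction.** Assumed success rates are 25% with neither intervention, 30% with either one, and x% with both. As written, b1 = logit(.30) - logit(.25) = .251 with SE .421, so power is .092 whatever x is.

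| x | interaction odds ratio | power as written | power averaged |
|---|---|---|---|
| 36% | 1.02 | .092 | .147 |
| 40% | 1.21 | .092 | .224 |
| 45% | 1.48 | .092 | .344 |
| 50% | 1.81 | .092 | .479 |

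**Hypothesis 1b with linear time.** Visits are assumed uniform over months 0-20 and 22-42. The phase means are 22 months apart, so the between-phase variance is 11² = 121 and the within-phase variance is 20²/12 = 33.3. The time-phase correlation is sqrt(121/154.3) = .885.

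| scenario | power as written | power averaged |
|---|---|---|
| 25% vs 35% (SE .69 vs .63) | .107 | .119 |
| x = 36% | .065 | .070 |
| x = 40% | .065 | .086 |
| x = 50% | .065 | .145 |

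**Continuous outcomes, d = .50, Hypothesis 1a.** Pre-training patients only, 4.5 per physician: SE = sqrt((.05 + 4/4.5)/24) = .198, power .68 with no interaction. The averaged effect keeps .915. If the averaged effect is .50 and the interaction is .2 or .5, the tested coefficient is .40 or .25, with power .49 or .23.

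**Aim 2, race by patient intervention.** With an equal race split there are 27 patients per race-arm-phase cell. As written with the three-way term in the model: SE = sqrt(.95 × 2 × (1/(27 × .1875) + 1/(27 × .2275))) = .83. Averaged over phases: .83/sqrt(2) = .59.

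**Simulation check.** GEE fits (24 × 9, exchangeable correlation, linear time in the model, 600 runs per scenario) gave .20 against .36 for Hypothesis 1a at 25% versus 35%. At x = 50% they gave .09 against .47 for Hypothesis 1a and .08 against .15 for Hypothesis 1b.

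**The case against.** The strongest reply is that simple effects may be what the sponsor wants. The Specific Aims and the Overview set the combined effect of the two interventions against the independent effect of each. Each intervention alone, plus an increment from having both, is exactly what 0/1 coding gives. On that reading, main effect is loose wording for a lower-order term. This reading is possible, but it leaves the plan undecided between two contrasts for its primary outcome. It also means the power section, which uses all 216 patients, does not describe the test.

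Other points:

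- **Coding.** It is unwritten, and Models for Aim 1 says it describes the models only in general terms. That stands, so 0/1 is an assumption here. It is the usual meaning of dummy-coded, and nothing in the plan points to another code.
- **Separate models.** Hypothesis 1a mentions fitting separate models, but this refers to continuous and binary outcomes. The text before it says the hypotheses share the same models.
- **Hypothesis 1b.** The gain from averaging is small once time is controlled. This stands.
- **Aim 2.** The order of entry is not stated. If the two-way race terms are tested before the three-way term enters, the race by patient-intervention coefficient is not limited to the pre-training phase. This stands, so that part is conditional. The planned probing of the race interactions does not alter the stated criterion.
- **Outcome form.** The self-reported decision may be analysed by multinomial regression, whereas the power figures above are for a binary outcome. The figures are therefore indicative for that model, but each of its logits has the same problem.

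**Conclusion.** The concern holds and should be fixed. Under 0/1 coding, the coefficients that decide Hypotheses 1a and 1b are not the main effects the plan says it examines, and the plan's own expected interaction pulls the two apart.

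The clear loss is for Hypothesis 1a, where the tested coefficient has about twice the variance of the averaged effect. For continuous outcomes, the stated power above .90 belongs to the averaged effect and not to the coefficient tested. The race by patient-intervention test loses precision to the same degree if the three-way term is in the model. For Hypothesis 1b the point is mainly one of meaning.

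The algebra needs only the 0/1 coding. The sizes also rest on 1:1 allocation, equal phases, the .95 variance factor and, for the interaction scenarios, assumed cell rates. Power for the binary primary outcome is low on either version; that is a separate problem and does not add to the weight of this one.

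**What to change.** State the estimand for Hypothesis 1a, Hypothesis 1b and the Aim 2 race interaction. To match the main effects the plan names, either code both interventions (and race in Aim 2) as -1/2 and +1/2, or pre-specify these tests as contrasts averaged over the other factor from the same model. Averaging keeps Hypothesis 1a a randomised comparison, since patients are randomised in both phases. Keep the product-term test for Hypothesis 1c, and report the four cell estimates as the effects of each intervention alone and combined. If simple effects are intended after all, say so and restate power on about 108 patients.

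The cost is one or two sentences in the analysis plan, with the same model and data. The change does not deliver the stated power above .99 or remove the collinearity of time with pre/post. Nor does it settle what the Hypothesis 1b coefficient means if the boosters listed under Control variables are the reminder cards given only after training.
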